4.6 SAFETY ANALYSES

Safety analyses will be based on all patients who received at least one administration (full or partial dose) of randomized study drug, with patients grouped according to the actual treatment received. Safety summaries will be presented by the treatment arm for all treated patients.

Safety will be assessed through descriptive summary of exposure to study treatment, seriousness and severity of AEs and adverse events of special interest (AESIs), changes in laboratory test results, death, discontinuation from study treatment, ECG and vital signs. These summaries will be produced for the entire study period (placebo-controlled study treatment period and safety follow-up period for patients not entering the open label extension study).

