3.1.1 Overall Study Design and Plan

This Phase III, randomized, double-blind, placebo-controlled, pivotal study is designed to confirm the efficacy and safety of PRM-151 in the treatment of patients with IPF during a 52-week period. At the end of this 52-week period, patients will be invited to enroll in *an* open-label extension study (Study WA42294) to receive treatment with PRM-151. Patients who do not enroll in the OLE study will be followed up for an additional 4 weeks (to Week 56, for safety monitoring).

The OLE study will provide patients with further study assessments and PRM-151 treatment on an ongoing basis. However, the OLE study will also consist of a long-term survival cohort, in which patients who do not want further study assessments or treatment can enroll (for long-term collection of survival data only).

[Figure 1](#) presents an overview of the study design. A schedule of activities is provided in [Appendix 1](#).

Figure 1 Study Schema

OLE = open-label extension; Q4W = once every 4 weeks.

^a Patients will have a final assessment visit at Week 52 (4 weeks after the final study drug infusion). For patients enrolling in the OLE study, this will also be their end of study visit.

^b Patients who do not enroll in the OLE study will have their final assessment visit at Week 52, followed by an end of study visit at Week 56 (8 weeks after the final study drug infusion).

Patients meeting the eligibility criteria for the study will be randomized to PRM-151 10 mg/kg Q4W or placebo. Efficacy will be evaluated through assessment of functional capacity as measured by FVC, 6MWD, other PFTs, and assessment of patients with respiratory events leading to hospitalizations, progression of disease, acute IPF exacerbations.

Patient reported outcomes (PROs) will be assessed using the SGRQ, UCSD-SOBQ, and EQ-5D-5L.

Dyspnea, fatigue, and SpO₂ will be assessed based on measurements taken during the 6MWT. For patients who require a HRCT scan during the screening period, an additional chest HRCT scan will be performed at Week 52. Patients who do not require a HRCT scan during the screening period (i.e., they already have a historic HRCT scan of acceptable quality performed within 12 months prior to screening) will not be required to perform a scan at Week 52.

Treated patients will be followed until the end of the 52-week study period unless the patient withdraws consent for follow-up or dies.

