- Concurrent use of nintedanib treatment versus pirfenidone treatment versus no concurrent treatment
- Region: China (including Hong Kong and Taiwan), North America (United States and Canada), Europe (including eastern Europe), Latin America, and Rest of World (including east Asia, Australia, and New Zealand)

All patients will have a final assessment visit at Week 52 (4 weeks after the final study drug infusion). Patients will be invited to enroll in an OLE study at this point (Study WA42294), and if they roll over into that study, the Week 52 visit will be considered their end of study visit. Patients who do not enroll in the OLE study will have their end of study visit at Week 56, in addition to the Week 52 visit (see [Table 1](#)).

Table 1 Final Assessment and End of Study Visits

	Last Infusion of Study Treatment	Final Assessment Visit	End of Study Visit
Patients enrolling in OLE study for ongoing PRM-151 treatment	Week 48	Week 52	Week 52
Patients enrolling in OLE study for survival follow-up only	Week 48	Week 52	Week 56
Patients not enrolling in OLE study	Week 48	Week 52	Week 56

OLE = open-label extension study (Study WA42294).

This study will enroll approximately 658 patients globally across all sites. Enrollment will be globally competitive. After completion of the global enrollment phase, additional patients may be enrolled in an extended China enrollment phase at sites in mainland China, Hong Kong, and Taiwan. The global population will include all patients enrolled during the global enrollment phase and the China subpopulation will include all patients *enrolled in China, Hong Kong, and Taiwan* (i.e., during both the global enrollment phase and the extended China enrollment phase).

Individuals who do not meet the criteria for participation in this study (screen failure) may be eligible for rescreening once for selected reasons. In addition, the screening period may be extended if a patient fails a test due to technical issues with the test and the patient will be allowed to repeat the test (e.g., lab sample hemolyzed and not able to be analyzed).

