- If the patient does not receive the scheduled dose within the specified visit window for the Week 4 visit or beyond, a protocol deviation will be documented, and the patient should be dosed as soon as possible within 3 weeks of the original scheduled visit.
- If the dose is delayed by > 3 weeks beyond the original scheduled visit (within 1 week of the next scheduled dosing visit), the delayed dose is considered a missed dose and should not be administered. Dosing should resume with the next dose (reloading of three doses, as described above) according to schedule.
- After a missed or delayed dose, patients should keep following the dates on the original dosing schedule, and visit dates should not shift, unless otherwise directed by the investigator or study team (additional visits to allow for reloading of three doses will need to be scheduled).

In exceptional situations and following consultation with the Medical Monitor, if patients cannot attend the study site for a scheduled infusion, administration of study drug may be permitted in other settings (e.g., at a different investigational site). Patient safety must be prioritized when utilizing off-site procedures (e.g., ensuring staff are appropriately qualified to deliver the infusion and are trained to monitor for and manage anaphylaxis and IRRs). In such circumstances, infusion-related safety data, safety laboratory assessments, and PK/PD samples may also be collected off-site.

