5.4.1 Adverse Event Reporting Period

Investigators will seek information on adverse events at each patient contact. All adverse events, whether reported by the patient or noted by study personnel, will be recorded in the patient's medical record and on the Adverse Event eCRF.

After informed consent has been obtained but prior to initiation of study drug, only serious adverse events caused by a protocol-mandated intervention (e.g., invasive procedures such as biopsies, discontinuation of medications) should be reported (see Section 5.5.2 for instructions for reporting serious adverse events). *All other medical occurrences that begin before the start of study treatment but after obtaining informed consent will be recorded on the General Medical History and Baseline Conditions eCRF, and not on the Adverse Event eCRF.*

After initiation of study drug, all adverse events will be reported until 8 weeks after the final dose of study drug.

Instructions for reporting adverse events that occur after the adverse event reporting period are provided in Section 5.7.

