Appendix 1: Schedule of Activities

ADA=anti-drug antibody; AE=adverse event; Discon.=discontinuation; DLCO=diffusing capacity for carbon monoxide; eCRF=electronic Case Report Form; EQ-5D-5L=EuroQol 5-Dimension, 5-Level Questionnaire; HRCT=high-resolution computed tomography; IPF=idiopathic pulmonary fibrosis; OLE=open-label extension; PCR=polymerase chain reaction; PD=pharmacodynamic; PK=pharmacokinetic; SGRQ=St. George Respiratory Questionnaire; SAE=serious adverse event; SARS-CoV-2=severe acute respiratory syndrome coronavirus 2; TB=tuberculosis; Treat.=treatment, UCSD-SOBQ=University of California, San Diego-Shortness of Breath Questionnaire.

- ^a Screening period is up to 4 weeks. Eligible patients can be randomized as soon as their screening assessments have been completed and all eligibility criteria have been confirmed. Randomization must occur prior to any baseline assessments being conducted on Visit 2.
- ^b Patients will have their final safety and efficacy assessments, including HRCT if applicable, at Week 52.
- ^c Patients not enrolling in the OLE study will return for an end-of-study visit at Week 56.
- ^d Treatment discontinuation visit should occur 4 weeks after final dose of study drug. Study discontinuation visit should occur 4 weeks after the treatment discontinuation visit (8 weeks after the final dose of study drug).
- ^e To allow for flexibility around weekends, holidays, and so on, the loading dose visits may occur over a time span of up to 8 days, with a minimum of 1 full calendar day between administration of doses (patients must not be dosed on consecutive days). In case one or more loading doses have been missed or delayed beyond the 8-day loading phase window, loading doses should be administered again at the next scheduled visit. No loading doses should be administered outside of the 8-day loading phase window.
- ^f Patients who discontinue study drug early will have \pm 2-week window to complete study visits.
- ^g Testing for active or latent TB should be conducted with an interferon gamma release assay during screening. Patients who have completed treatment for active or latent tuberculosis within 6 months prior to screening, and have no evidence of recurrent disease, do not need to be tested.
- ^h On dosing days, vital signs should be completed predose (within 60 minutes prior to dosing), every 15 minutes during infusion, and 30–60 minutes postdose.

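### Table 1 plans a Week 56 visit for patients who join the OLE for survival follow-up only, but the schedule, the design text and SAP 4.6 split patients only by OLE entry, putting that visit and the reporting of Week 52–56 events at risk

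*SAP*

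**What the plan says.** The OLE (Study WA42294) has two routes. One continues PRM-151 with assessments. In the other, "patients who do not want further study assessments or treatment can enroll (for long-term collection of survival data only").

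The visit rules for patients leaving the 52-week period are these:

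- **Protocol 3.1.1, Table 1** has three rows. The row "Patients enrolling in OLE study for survival follow-up only" shows last infusion Week 48, final assessment Week 52 and end of study Week 56. Only the row for ongoing PRM-151 treatment ends at Week 52.
- **Protocol 3.1.1, text above Table 1**, speaks of OLE patients as one group: "if they roll over into that study, the Week 52 visit will be considered their end of study visit". It then refers to Table 1. The synopsis has the same rule without the table.
- **Protocol 3.1.1, opening text**: "Patients who do not enroll in the OLE study will be followed up for an additional 4 weeks (to Week 56, for safety monitoring"). Figure 1 footnotes a and b use the same two-way split.
- **Protocol Appendix 1, footnote c**: "Patients not enrolling in the OLE study will return for an end-of-study visit at Week 56".
- **Protocol 4.6.2** sets the completion or discontinuation visit at 8 weeks after the final dose, without mentioning the OLE, and points to the Week 56 column of Appendix 1.
- **Protocol 5.4.1**: "all adverse events will be reported until 8 weeks after the final dose of study drug". Section 5.5.2.2 repeats this for serious adverse events and events of special interest. Neither has an OLE exception.
- **SAP 1.2** and its figure footnotes repeat the two-way split and define the placebo-controlled treatment period as Day 1 to Week 52.
- **SAP 4.6** bounds the safety summaries by that treatment period plus the "safety follow-up period for patients not entering the open label extension study".

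**The concern.** Survival-only enrollees do enter the OLE, but they receive no drug and no assessments there. Under any rule that asks only whether a patient enrolled, they are grouped with patients who continue treatment. A site that schedules from Appendix 1 would not book their Week 56 visit. A programmer who applies SAP 4.6 as written would cut their safety data at Week 52, even where the site followed Table 1 and recorded later events.

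At stake are the Week 56 assessments, such as laboratory tests (Appendix 1) and anti-drug antibody samples (Appendices 2 to 4), and the tabulation of events that the protocol requires sites to report. The survival-only OLE cohort collects survival data only, so it would not supply what this study omits.

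**Working it through.** No sample-size or power figure is involved. The check is visit arithmetic and a comparison of passages.

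**1. The plan's own intervals.** Last infusion Week 48, final assessment Week 52, end of study Week 56 (Table 1):

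- 52 − 48 = 4 weeks
- 56 − 48 = 8 weeks

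Both agree with the Figure 1 footnotes, and the second matches the 8-week reporting window in 5.4.1 and 5.5.2.2.

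**2. Part of the reporting window that falls after Week 52.** For a last dose actually given in week L, the window closes at L + 8. The part after Week 52 is max(0, L + 8 − 52), and its share is that number divided by 8.

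| Last dose (week) | Window closes (week) | Weeks after Week 52 | Share of window |
|---|---|---|---|
| 36 | 44 | 0 | 0% |
| 40 | 48 | 0 | 0% |
| 44 | 52 | 0 | 0% |
| 48 | 56 | 4 | 50% |

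For a Week 48 last dose this is 28 of 56 days.

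**3. What each source implies for a survival-only enrollee last dosed at Week 48.**

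| Source | Last visit or cut-off | Weeks after last dose |
|---|---|---|
| Protocol Table 1 | Week 56 | 8 |
| Protocol 4.6.2 | 8 weeks after final dose | 8 |
| Protocol 5.4.1, 5.5.2.2 (event reporting) | 8 weeks after final dose | 8 |
| 3.1.1 text, synopsis, Figure 1 footnotes | Week 52 | 4 |
| Appendix 1 footnote c | Week 56 not assigned | 4 |
| SAP 1.2 | Week 52 | 4 |
| SAP 4.6 (summaries) | Week 52 | 4 |

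**4. Whether another SAP passage removes the limit.** SAP 4.6.2 says when an event starts to count as treatment-emergent but gives no end date, so the period in SAP 4.6 is the only stated upper bound. The SAP introduction says that it supersedes the protocol's analysis plan, so the protocol does not override SAP 4.6. SAP Appendix 1 does not list a shorter safety period among the changes from the protocol.

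**5. A separate timing question.** Under Protocol 4.3.2.1, for a dose that misses its window, "the patient should be dosed as soon as possible within 3 weeks of the original scheduled visit", and visit dates normally stay fixed unless the investigator or study team directs otherwise. A Week 48 dose given at Week 51 leaves 56 − 51 = 5 weeks to a Week 56 visit, against 8 weeks in 4.6.2 and 5.4.1, a difference of 3 weeks. This arises whatever the patient's OLE choice.

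**The case against.** The strongest reply is that the protocol already covers these patients. Table 1 names them, the 3.1.1 text refers to Table 1, and 4.6.2 requires the 8-week visit without exception. Reporting of adverse events, serious events and events of special interest runs 8 weeks for everyone. SAP 4.6 says that the summaries cover the whole study, with the OLE restriction only in a parenthesis, and SAP 4.6.2 sets no cut-off.

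Much of this stands, and it rules out several stronger readings that a reader might infer:

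- *That Table 1 is the only support for the visit.* It is the only place that names the cohort, but 4.6.2 also supports an 8-week visit. However, 4.6.2 sends the reader to Appendix 1, where footnote c restricts Week 56 to patients not enrolling, so it does not settle the conflict.
- *That the safety data are lost.* The reporting duty remains, so the data are at risk. Still, 5.4.1 has investigators ask about events at patient contacts, and without a Week 56 visit no contact is scheduled and no Week 56 samples are drawn.
- *That half the window is affected for every such patient.* This holds only for a Week 48 last dose.
- *That these patients are the ones who tolerated the drug badly.* No passage says so, and those who stopped by Week 44 have no reporting window left after Week 52.
- *That the late-dose question is part of the same fault.* It is separate, and the allowance for directed changes to visit dates partly covers it.

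The point about the SAP parenthesis does not remove the problem. The parenthesis is what defines the period, and nothing else in the SAP sets an upper limit.

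**Conclusion.** The inconsistency is real and should be corrected before the safety tables are programmed. Table 1 and 4.6.2 give survival-only OLE enrollees a visit 8 weeks after the last dose; the synopsis, the 3.1.1 text, the Figure 1 footnotes, Appendix 1 footnote c and SAP 1.2 do not. SAP 4.6, taken literally, leaves their Week 52–56 events out of the summaries although those events are reportable.

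The size is up to 4 of 8 weeks (28 of 56 days) per patient last dosed at Week 48, and zero for a last dose at Week 44 or earlier. The number of patients cannot be derived: the documents give no expected size for the cohort, so no patient-year figure or effect on event rates is claimed. The conclusion assumes that sites follow the schedule of activities and programmers follow SAP 4.6 as worded.

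**What to change.** 1. **Protocol.** Reconcile the synopsis, the 3.1.1 text, the Figure 1 footnotes and Appendix 1 footnote c with Table 1, so that each separates OLE patients who continue study drug from those followed for survival only. Make the same distinction in SAP 1.2.
2. **SAP 4.6.** Replace the condition of not entering the OLE with the condition of not receiving study drug in the OLE. Events collected in the 8-week reporting window are then summarized for the survival-only cohort. This change is needed even while the visit wording is being settled, because the reporting window already applies to these patients.
3. **Separately**, reconcile the late-dose provision in Protocol 4.3.2.1 with the 8-week timing in 4.6.2 and 5.4.1.

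Items 1 and 2 cost wording in the protocol and SAP. They add no visit beyond what Table 1 already plans and do not touch the efficacy analysis or the sample size. For item 3 it is enough that the passages agree.

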4.6.1 Extent of Exposure

Extent of exposure to study drug (zincpentraxin alfa or placebo) will be summarized descriptively (mean, standard deviation, median, range, and proportions where appropriate) for the following measures:

- Number of patients exposed
- Treatment duration (weeks), measured from date of first administration at Baseline Day 1
- Cumulative number of infusions = total number of non-zero infusions
- Cumulative volume of infusion received = total volume of non-zero infusions
- Number of missed infusions
- Number of patients receiving reloading infusions
- Number of infusion cycles, defined as either up to 3 loading or reloading infusion or 1 regular infusion

Extent of exposure to zincpentraxin alfa will also be summarized by drug generation using the above measures.

Exposure to concurrent use of pirfenidone or nintedanib will also be summarized descriptively by treatment group.

4.6.2 Adverse Events

All verbatim (“investigator-reported”) AE terms will be assigned a standardized term (the “preferred term”) and a superclass term using the most current version of the Medical Dictionary for Regulatory Activities (MedDRA) thesaurus terms, and AE severity will be graded according to National Cancer Institute (NCI) Common Terminology Criteria for Adverse Events (CTCAE) v5.0 scale. A by-patient AE data listing including onset study day, duration, preferred term, treatment, severity, relationship to treatment, treatment for AE, action taken, and outcome will be provided.

All AEs, serious adverse events (SAEs), AEs leading to death, AESIs, and AEs leading to study treatment discontinuation that occur during or after the first dose of study treatment (i.e., treatment-emergent adverse events) will be summarized by preferred term and severity grade as appropriate. An exacerbation or worsening of a pre-existing condition will be considered treatment-emergent only if the most extreme intensity is greater than the intensity at baseline (i.e., the intensity for a given AE increases and its end date is on or after the date of the first dose). For events of varying severity, the highest grade will be used in the summaries. Listings of AEs, SAEs, and AESIs will also be produced. Any non-treatment emergent SAEs will also be listed separately.

Summary tables of the cumulative incidence of safety outcomes will be provided for the treatment and placebo arms independently. Safety outcomes of interest include, but are not limited to:

- AEs and SAEs of any grade
- AEs (any grade) with a difference in incidence between the treatment and placebo arm
- AEs by highest NCI CTCAE v.5.0 grade
- Severe AEs (NCI CTCAE v.5.0 Grade 3 or above)
- AEs leading to death
- AEs leading to study treatment discontinuation
- AEs leading to drug interruption
- AEs leading to withdrawal from study
- Treatment related AEs and SAEs
- AESIs
- Common AEs, i.e., those occurring in at least 5% of patients in either arm
- Suspected Infusion Related Reaction (all grades)

Summaries of safety data by baseline concurrent anti-fibrotic therapy and zinpentraxin alfa drug generation will be provided as appropriate.

The within-arm cumulative incidence and the difference in cumulative incidence between arms, along with the 95% CIs, will be summarized in a forest plot for the following safety outcomes: all AEs, all severe AEs, all SAEs, all AEs leading to treatment discontinuation, all AEs determined to be related to study drug, deaths, and the most frequent individual AEs (by preferred term).

Deaths and cause of death will be summarized and a listing of patients who died during the study will be provided.

Summaries of confirmed or suspected COVID-19 AEs and AEs associated with COVID-19 will also be provided.

A listing of all pregnancies will be presented.

AESIs for this study are as follows:

AESIs related to drug development in general:

- Cases of potential drug-induced liver injury that include an elevated alanine aminotransferase (ALT) or aspartate aminotransferase (AST) in combination with either an elevated bilirubin or clinical jaundice, as defined by Hy's Law (see Section 5.4.5.7 of the Protocol) or if the patient is reported to have the preferred term of 'drug-induced liver injury'
- Suspected transmission of an infectious agent by the study drug, as defined below:
Any organism, virus, or infectious particle (e.g., prion protein transmitting transmissible spongiform encephalopathy), pathogenic or non-pathogenic, is considered an infectious agent. A transmission of an infectious agent may be suspected from clinical symptoms or laboratory findings that indicate an infection in a patient exposed to a medicinal product. This term applies only when a contamination of the study drug is suspected. Such events will be retrieved if a patient is reported to have the MedDRA preferred term of 'suspected transmission of an infectious agent via product' or 'transmission of an infectious agent via product'

AESIs relevant to zinpentraxin alfa:

- Suspected Infusion Related Reaction with NCI CTCAE Grade ≥ 2 : The risk of IRR associated with zinpentraxin alfa is inherent in it being the recombinant form of a naturally occurring human protein. The subset of the potential risk of IRR (Grade ≥ 2) has been categorized as drug specific AESI for close monitoring. Infusion Related Reaction includes all the cases if meet both the following criteria:
(i) any events onset during the infusion or within 24 hours from the end of study infusion (ii) causality: not unrelated (related or missing). However, further analysis

will be performed to identify true cases of IRR based on medical judgement and confirmation provided by the investigators.

- Suspected anaphylactic or hypersensitivity reactions (all grades): Anaphylactic and hypersensitivity reactions are considered potential risk for all biologic medications including zinpentraxin alfa. Potential cases of anaphylactic, anaphylactoid, and hypersensitivity reactions will be identified and sent for adjudication by an independent Anaphylaxis Adjudication Committee (see Section 1.2.2.5). Events will be identified using the Standardized MedDRA Query (SMQ Wide) 'Anaphylactic reaction' and MedDRA gastrointestinal symptoms event terms consistent with Sampson criteria. In addition, all cases flagged by the investigator as an AESI under the criterion 'Suspected anaphylactic or hypersensitivity reactions' or with an AE term of "anaphylaxis", "hypersensitivity" or for which an investigator has assessed that the event represents "known or suspected" anaphylaxis will be considered for adjudication. Members of the AAC review blinded data to adjudicate cases as anaphylaxis per Sampson's Criteria and for relatedness to study drug. A detailed description of the process for identification of potential events and data flow is provided in the AAC Charter. Events adjudicated by the AAC as meeting Sampson's Criteria for anaphylaxis and relatedness to study drug will be summarized. Additionally, a listing of all possible cases of anaphylaxis will be produced.
- Acute or suspected exacerbation of IPF (all grades): Acute exacerbation of IPF is defined as an acute, clinically significant respiratory deterioration characterized by evidence of new widespread alveolar abnormality, marked by the following diagnostic criteria ([Collard et al. 2016](#)):
 - Previous or concurrent diagnosis of IPF
 - Acute worsening or development of dyspnea typically <30 days in duration
 - Computed tomography with new bilateral ground-glass opacity and/or consolidation superimposed on a background pattern consistent with UIP pattern
 - Deterioration not fully explained by cardiac failure or fluid overload
- Acute exacerbations of IPF are further categorized as triggered acute exacerbation or idiopathic acute exacerbation, depending on whether an underlying trigger for acute exacerbation is found (e.g., infection, post-procedural/postoperative, drug toxicity, aspiration). There is no evidence to suggest acute or suspected exacerbation of IPF is a risk associated with zinpentraxin alfa. This was categorized as an AESI based on the feedback received through the Voluntary Harmonization Procedure.
- An independent, blinded Clinical Adjudication Committee review all available data for all potential cases of acute exacerbations of IPF. The committee determines if the reported events meet the criteria of an acute exacerbation of IPF or a suspected acute exacerbation. Events that are clinically considered to meet the definition of acute exacerbation of IPF but fail to meet all four diagnostic criteria owing to the

missing computed tomography data are termed “suspected acute exacerbations of IPF”.

The data collected from the already completed Phase I and Phase II trials of zinpentraxin alfa do not suggest that the frequency or nature of the AESIs listed above are serious enough to potentially impact regulatory decision-making.

